Improving Uptake of Genetic Cancer Risk Assessment in African American Women - Video

Title: Improving Uptake of Genetic Cancer Risk Assessment in African American Women – Video

Protocol # NCI-2019-0489

NCT# NCT 04476654

Current IRB Approval Date 8.9.23

Study Overview

Genetic counseling and testing (GCT) provides invaluable information for women who are at risk of hereditary breast and/or ovarian cancer (HBOC). Black women underutilize GCT compared to White women. This study conducted an RCT to test the efficacy of a culturally-tailored theory-based video intervention aimed to address key psychosocial factors (emotions, ambivalence) to improve the uptake of genetic counseling in Black women at increased risk of HBOC. Findings from this study may offer an opportunity to engage at-risk Black women regarding genetic counseling through a multi-center trial and ultimately address the disparity in genetic counseling uptake that exists between Black and White women.

Detailed Description

Breast cancer (BC) is the most frequently diagnosed cancer in African American women (hereafter referred to as "Black"), and their cancer mortality is higher than other racial/ethnic groups in the United States (US). Compared to non-Hispanic Whites, Black women are diagnosed younger and with more advanced breast cancer. When diagnosed with BC, Black women present more often with triple-negative breast cancer (TNBC), an aggressive disease defined by the absence of estrogen and progesterone receptors and human epidermal growth factor (HER)-2 expression. TNBC has been associated with pathogenic BRCA1 variants. Racial disparities also exist for women with ovarian cancer, the most lethal of the gynecologic cancers. Among women with advanced ovarian cancers, up to 21% are associated with inherited pathogenic mutations, the most common of which is BRCA1. Women who carry a pathogenic BRCA variant (PV) have a lifetime breast cancer risk of 55-70% and a lifetime ovarian cancer risk of up to 44%. The National Comprehensive Cancer Network (NCCN) recommends referral for Hereditary Breast and Ovarian Cancer (HBOC) genetic counseling and testing (GCT) for women at risk of carrying a BRCA PV. GCT provides women with the information needed to make informed decisions to reduce their cancer risk, yet Black women are less likely to use GCT than Whites. There is a dearth of interventions to address this issue and produced results are mixed and modest. Awareness of a positive result can inform treatment decisions for cancer patients and risk management in survivors or women unaffected by cancer.

Reasons for the lower uptake of GCT in Black women are multi-factorial and include access, knowledge, psycho-social factors, and may vary by cancer status (affected versus unaffected). There are substantial scientific gaps regarding effective interventions to address the sub-optimal uptake of GCT in Black women. To be effective, GCT interventions should be anchored within the needs and cultural values of their audience. While improving knowledge about GCT and one's individual risks is important, interventions that only address knowledge may not enhance uptake, as risk information evokes emotional reactions that are often stronger predictors of behaviors than cognitive factors.

Notably, this team has identified factors that contribute to Black women's uptake of GCT. In preliminary studies, researchers found that self-efficacy in making decisions about GCT and medical mistrust were associated with GCT uptake. Low knowledge among Black BC survivors at risk of HBOC has also been found. Anticipated negative emotions to GCT have been associated with lower uptake. Similar studies suggest that Black women report emotions related to fear of being singled out and the fear of being hopeless. Because most interventions have

focused solely on knowledge or access, the proposed study makes a considerable shift in the field by additionally targeting emotions and ambivalence and developing a media-based risk communication tool.

Guided by two evidenced-based theories and preliminary data, this was a two-phased mixed methods study. In Phase I (months 1-7), formative research and preliminary data were used to develop the script for the GCT video. The script was reviewed by GCT experts (n=4) and piloted in two focus groups (n=16), followed by a staged reading to make final refinements. In Phase II (months 8-24), a two-arm randomized trial (RCT) to compare GCT uptake and psycho-social outcomes between 50 at-risk Black women receiving printed Susan G. Komen developed GCT literature (control group) (n=25) or a tailored YouTube video intervention (n=25) was be conducted. All women were referred to an appointment scheduler who assisted them with making an appointment with a genetic counselor. Participants completed a baseline survey and follow-up assessment. The primary outcome was genetic counseling uptake, and receipt testing at 3 months was explored. Specific aims are to:

Aim 1. Develop a YouTube video using formative data for Black women at risk for HBOC.

Aim 2. Evaluate the efficacy of the intervention by comparing outcomes between women in the YouTube intervention arm vs. the control group arm. H.2.1. Women in the intervention group (vs. control group) had higher genetic counseling uptake. H.2.2. Women in the intervention group (vs. control group) was report higher knowledge, higher self-efficacy, higher endorsement of positive attitudes, and positive anticipated emotions about GCT. H.2.3. Most women ($\geq 75\%$) were satisfied with the experimental intervention.

Enhancing GCT in at-risk populations is a national priority. Given trends toward panel testing and other genomic advances, there is potential for existing disparities to widen. Findings inform new strategies for behavioral interventions for Black women and a larger trial. If successful, the intervention could be easily disseminated, broadening its reach to affected and unaffected women.

This study meets the Healthy People 2020 goals to enhance GRCA in at-risk populations, and the national priorities to increase diversity in genetics research participation and incorporate emotions into cancer research. Findings informed new strategies for behavioral interventions targeting African Americans in a larger trial.

Participation Criteria

Inclusion Criteria:

- Must be at least 18 years of age
- Must be at high risk for hereditary breast or ovarian cancer
- Must identify as Black/African American
- Must be a woman
- Referred to a genetic counselor for the purpose of being at high risk of carrying a hereditary breast and/or ovarian cancer mutation

Improving Uptake of Genetic Cancer Risk Assessment in African American Women - Video

Genetic Counselors:

- Must be at least 18 years of age
- Must be qualified
- Must be approved by the PI

Exclusion Criteria:

- Under the age of 18
- Race other than Black/African American
- Do not have a high risk for hereditary breast or ovarian cancer

Genetic Counselors:

- Under 18
- Not qualified
- Not approved by the PI

Participant Group/Arm	Intervention/Treatment
No Intervention: Fact Sheet Arm Komen print materials about genetic counseling and testing will be given to women.	
Active Comparator: YouTube Video Arm Participants in this arm will receive the culturally tailored video either via a YouTube link or a DVD.	
Behavioral: YouTube Video Arm
 
• Participants (n=25) watched a 20-minute YouTube video that described the genetic counseling and testing process and risk/benefit information in a culturally relevant format. Participants completed pre and post-assessments. After the session, participants interested in pursuing genetic counseling and testing services were referred to a patient navigator who navigated participants to identify no-cost or low-cost services.

What is the study measuring?

Outcome Measure	Measure Description
Rate of genetic counseling and testing uptake.	Our primary outcome was for participants to receive genetic testing and counseling. Investigators were able to see if a participant had scheduled a genetic testing appointment within the VCU Health appointment system.

Secondary Outcome Measures

Outcome Measure	Measure Description	Time Frame
Knowledge Scale - Genetic counseling and testing knowledge.	The investigators tested general knowledge about hereditary breast and ovarian cancer	Within one hour before the intervention and within one hour post-intervention.
Self-efficacy Scale	The investigators tested self-efficacy in genetic counseling services.	Within one hour before the intervention and within one hour post-intervention.
Emotional Ambivalence Scale	The investigators tested the emotional ambivalence about participating in genetic counseling services.	Within one hour before the intervention and within one hour post-intervention.

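### The primary outcome is defined as different events in different places, and no time window is clearly attached to it

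*Protocol*

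**What the plan says.** **Protocol, Study Overview.** The aim is to "improve the uptake of genetic counseling in Black women at increased risk of HBOC". Testing is not part of that target.

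**Protocol, Detailed Description.** "The primary outcome was genetic counseling uptake, and receipt testing at 3 months was explored". Hypothesis H.2.1 matches this: "Women in the intervention group (vs. control group) had higher genetic counseling uptake". The same section describes the help given with booking: "All women were referred to an appointment scheduler who assisted them with making an appointment with a genetic counselor".

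**Protocol, What is the study measuring?** The primary measure is named "Rate of genetic counseling and testing uptake". Its description opens with "Our primary outcome was for participants to receive genetic testing and counseling" and continues with the only ascertainment given: "Investigators were able to see if a participant had scheduled a genetic testing appointment within the VCU Health appointment system". As supplied, this row has no time frame, whereas each secondary outcome has one.

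**SAP, Data Analysis, Statistical Design and Power.** The quantity to be estimated is the between-group difference in the proportion obtaining GT. The next sentence says patient records will show whether participants seek GT. The abbreviation is not defined in the text available. The stated purpose is feasibility and effect-size estimation for a later confirmatory trial, with 25 women per group.

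**The concern.** Being counseled, being both counseled and tested, and having a testing appointment on the calendar are different events. A woman can have one without the others, so the uptake rates and the difference between arms can change with the event counted.

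The estimated difference is what the pilot is meant to hand to the confirmatory trial, and it cannot be used for planning unless its event is known. The Study Overview also presents the trial as an efficacy test ("This study conducted an RCT to test the efficacy of a culturally-tailored theory-based video intervention"), and H.2.1 is the hypothesis under test. If scheduled testing appointments were what was counted, H.2.1 would not have been tested.

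Without a window, the yes/no status of a woman counseled late also depends on when the records were searched.

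**Working it through.** This is a question of definition, so the main check is to set the statements side by side.

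| Place | Event | Role of testing | Window |
|---|---|---|---|
| Study Overview | Counseling uptake | Not mentioned in the aim | None |
| Detailed Description | Counseling uptake | Exploratory | 3 months, which grammatically qualifies testing |
| H.2.1 | Counseling uptake | None | None |
| Outcome table, name and first sentence | Counseling and testing, received | Part of the primary outcome | None in the supplied text |
| Outcome table, second sentence | Testing appointment scheduled at VCU Health | The only event described | None in the supplied text |
| SAP | GT obtained, then GT sought | Unclear, GT undefined | None in the supplied text |

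Next, code individual women under each reading.

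| Woman | Counseling uptake (H.2.1), read as counseling received | Both received | Testing appointment scheduled |
|---|---|---|---|
| Counseled, declines testing, none booked | Yes | No | No |
| Books testing, attends nothing | No | No | Yes |
| Counseled and tested outside VCU Health | Yes | Yes | Not seen |

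No two columns agree for all three women, so two analysts could code the same woman in opposite ways.

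**What the choice can do to the estimate.** The only numerical input from the documents is n = 25 per arm. The sample size was set on practical grounds, with no event rates, significance level or power stated, so there is no planned figure to reproduce beyond 25 + 25 = 50.

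- One woman is 1/25 = 0.04, or 4 points in her arm's rate.
- Change in the difference = (net reclassified in video − net reclassified in control)/25. It is zero if the same net number moves in both arms.
- If one event is r times as common as another in both arms, the difference scales by r, because r·pV − r·pC = r·(pV − pC).

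Illustration; all counts and values of r are assumed:

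| Case | Video | Control | Difference | Wald 95% half-width |
|---|---|---|---|---|
| Base | 10/25 | 5/25 | 20 points | 24.8 points |
| r = 0.6 | 6/25 | 3/25 | 12 points | 21.0 points |
| r = 1.4 | 14/25 | 7/25 | 28 points | 26.2 points |
| 2 more women in each arm | 12/25 | 7/25 | 20 points | not computed |

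Base half-width: 1.96 × √(0.4 × 0.6/25 + 0.2 × 0.8/25) = 1.96 × √0.016 = 0.248.

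The assumed shifts of 8 points are smaller than the sampling error. The problem is therefore which quantity is being estimated. A larger confirmatory trial would narrow the interval but would still need to know which event to count.

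**The case against.** The strongest reply is that only one contradiction is certain: counseling alone against counseling plus testing. On this view the scheduling sentence reports what investigators could see and is not a counting rule. The testing appointment may be a loose name for the visit with the genetic counselor, since no separate testing visit is described. GT may be defined in the part of the SAP that was not available, and a time-frame column may have been lost when the table was extracted. As a pilot sized on practical grounds, the trial has no power calculation that depends on the event.

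Some of this stands. Loose naming is possible for both the appointment and GT, and the window point is limited to the text supplied: the 3 months could be read as covering counseling too, although the sentence does not say so.

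It does not remove the problem. The scheduling sentence sits in the description of the primary measure and is the only ascertainment the protocol gives there. Even if it is set aside, the Detailed Description and the outcome table still disagree on whether testing belongs to the primary outcome. Pilot status does not help either, because the estimated difference is the pilot's main product.

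It is also fair to say that H.2.1 speaks only of uptake and does not itself specify an attended visit. Reading uptake as receipt draws on the outcome table's own verb.

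**Conclusion.** The concern holds, and the plan is wrong as written. The primary event is inconsistent within the protocol, and the available SAP text does not resolve it. Confidence is high on the event. The missing window is less certain, because part of the SAP was not available and a lost table column cannot be excluded.

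The direction and size of any effect on the result cannot be derived from the documents. The exact statement is 4 points per net woman reclassified in one arm. The 12-point and 28-point figures rest on assumed counts and an assumed ratio common to both arms, and the shift can be zero. The sample size is not called into question by this point.

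**What to change.** 1. State one primary endpoint in both documents, in line with H.2.1: genetic counseling received (visit attended, yes/no, from patient records), after randomisation and within one stated window. Three months is the only horizon the supplied protocol text offers.
2. Make scheduling an intermediate outcome and keep receipt of testing at 3 months exploratory.
3. Align the measure's name and both sentences of its description in the outcome table. In the SAP, define GT and replace the obtain and seek wording with the chosen event.
4. The protocol is largely in the past tense. If outcome data have already been seen, do not present the aligned endpoint as prespecified. State which definition was used and when it was fixed, and report scheduled, counseled and tested by arm.
5. Say how visits outside VCU Health are handled. The arm table has a navigator helping women find free or cheap services, and mentions this only in the video-arm row, so missed visits could differ by arm. If outside visits cannot be captured in the same way in both arms, label the endpoint as counseling received within VCU Health and state that it may under-count.

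The cost is wording in two documents and one by-arm table, assuming attendance and visit dates are in the patient records. If data have been seen, choosing the endpoint now is itself a post-data choice, so the change must be dated and disclosed.

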## Statistical Analysis Plan

**Data Analysis, Statistical Design and Power.** This study is designed to evaluate feasibility and to estimate effect sizes for a future planned confirmatory RCT. As such, the sample size calculation is based on practical considerations. van Belle and Julious have both recommended a minimum sample size of twelve per group for pilot studies. This is based on the fact that the precision of the estimate of the mean and variance greatly increases up to a sample size of twelve at which point the decrease becomes less dramatic. Although these recommendations were based on continuous outcomes, the same logic applies to binary outcomes as the square root of N also appears in the denominator for the test of proportions. With a sample size of 25 per group we will have an adequate sample to estimate the difference in the proportion of participants who obtain GT between groups. No attrition is expected for the primary outcome as patient records will be used to determine if participants seek GT.

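### Do the protocol's efficacy wording and the SAP's feasibility wording put the 50-woman trial at odds with itself?

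*SAP*

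**What the plan says.** The SAP's single section, Statistical Analysis Plan, opens with the purpose: "This study is designed to evaluate feasibility and to estimate effect sizes for a future planned confirmatory RCT". The size follows from that: "As such, the sample size calculation is based on practical considerations". It cites a rule of thumb of at least twelve per group for pilot studies, notes that the rule was derived for continuous outcomes, and argues that it carries over to proportions because precision again depends on the square root of N. It then concludes: "With a sample size of 25 per group we will have an adequate sample to estimate the difference in the proportion of participants".

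The protocol speaks of efficacy. Its Study Overview says "This study conducted an RCT to test the efficacy of a culturally-tailored theory-based video intervention". Aim 2, in the Detailed Description, is to "Evaluate the efficacy of the intervention by comparing outcomes between women in the YouTube intervention arm vs. the control group arm", and H.2.1 reads "Women in the intervention group (vs. control group) had higher genetic counseling uptake".

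The protocol also looks beyond this trial. The Study Overview says "Findings from this study may offer an opportunity to engage at-risk Black women regarding genetic counseling through a multi-center trial", and the end of the Detailed Description says "Findings inform new strategies for behavioral interventions for Black women and a larger trial".

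**The concern.** Two things look wrong at first.

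- **Purpose.** The same 50 women serve a feasibility and effect-size study in one document and a test of efficacy in the other. The visible protocol text never uses the words pilot or feasibility and does not call H.2.1 preliminary. Someone who read only the protocol might take a non-significant result as evidence that the video does not work, or a significant one as proof that it does.
- **Precision.** The SAP calls 25 per group adequate for estimating a difference in proportions but gives no interval width and no assumed uptake rate. The square-root-of-N argument shows that precision improves with size, not what precision 25 per group buys.

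At stake is interpretation. A moderate true gain could be dismissed. A result picked out because it was significant could overstate the effect and lead to a confirmatory trial that is too small.

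**Working it through.** **Inputs from the documents.** 25 per arm, 50 in total (protocol, Detailed Description; SAP). Pilot minimum of 12 per group (SAP). No attrition expected for the primary outcome (SAP). The visible text states no alpha, sidedness, test, control rate, target difference, power or interval width. Every rate below is therefore an assumption, as are the 5% level and the 95% interval.

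**The plan's own figure.** There is no calculation to reproduce. The only checks available are 25 + 25 = 50, which agrees with the protocol, and 25 ≥ 12, which meets the cited minimum.

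**Read as an efficacy test.** I enumerated all 26 × 26 outcomes of two independent Bin(25, p) counts and summed the probability of p ≤ 0.05, two-sided, for Fisher's exact test and the uncorrected chi-square test.

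| True gain | Fisher, control 5% | Fisher, control 10–50% | Chi-square, control 5% | Chi-square, control 10–50% |
|---|---|---|---|---|
| 20 points | 37% | 23–31% | 55.5% | 33–45% |
| 30 points | 70% | 51–59% | 83% | 62–73% |
| 40 points | 90% | 78–83% | 95.5% | 86–91% |

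Power is low for a 20-point gain unless control uptake is very low and the test is chi-square. H.2.1 is directional, and a one-sided 5% chi-square test would have 68% power for 20 points at 5% control uptake and 57% at 10%. None of this misses a target in the plan, because the plan sets no target power.

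**Read as estimation, the SAP's stated purpose.** The simple Wald half-width is 1.96 × √[p₁(1−p₁)/n + p₂(1−p₂)/n].

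- 10% in both arms, n = 25: 1.96 × √(0.09/25 + 0.09/25) = 0.166. With n = 12 it is 0.240.
- 20% vs 40%, n = 25: 1.96 × √(0.16/25 + 0.24/25) = 0.248. With n = 12 it is 0.358.
- 50% in both arms, n = 25: 1.96 × √(0.25/25 + 0.25/25) = 0.277. With n = 12 it is 0.400.

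Going from 12 to 25 per arm multiplies the width by √(12/25) = 0.69. The expected half-width of the Newcombe interval, averaged over all outcomes, is 16.2, 18.5, 21.8, 23.9 and 25.4 points at 5%, 10%, 20%, 30% and 50% in both arms. It is 21.3 points at 10% vs 30% and 23.4 at 20% vs 40%.

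**What one result would look like.** Take 10/25 on video and 5/25 on print, a difference of 0.20. The Wilson limits are 0.234 to 0.593 and 0.089 to 0.391.

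- Lower limit: 0.20 − √[(0.40 − 0.234)² + (0.391 − 0.20)²] = −0.05.
- Upper limit: 0.20 + √[(0.593 − 0.40)² + (0.20 − 0.089)²] = 0.42.

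Fisher p = 0.22; chi-square p = 0.12. The interval of −5 to +42 points shows by itself that the result is inconclusive.

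**Exaggeration.** If the true gain is 20 points, favourable significant results average 30 to 38 points (Fisher) or 27 to 35 (chi-square) for control rates of 5% to 50%. If it is 40 points, they average 42 to 45 or 41 to 43.5, which is slight. The inflation comes only from selecting on significance. The average over all results, significant or not, equals the true gain, because a difference in sample proportions is unbiased.

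**The case for a change.** The best case for a change is that the conflict can be seen on the page and would cost only wording to remove. An efficacy trial can also lead to a larger one, so the protocol's references to later work do not by themselves make H.2.1 preliminary. The word adequate carries weight that no number supports, and a reader who skips the SAP has little to temper the efficacy language.

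Three parts of this stand. The wording differs, the visible protocol text does not label the trial a pilot, and a stated interval width would be better practice.

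The rest goes too far. It is not true that nothing tells the reader how to weigh the result: the SAP does so in its first sentence and derives the sample size from it. Testing or evaluating efficacy is not the same as claiming confirmation, and a pilot may state a directional hypothesis. The protocol also has features of a preliminary study that the objection passes over: Phase I develops and pilots the script, and H.2.3 sets an acceptability benchmark of at least 75% satisfied. The low-power figures judge the trial on a use that the SAP does not claim for it. The exaggeration argument needs both a modest true gain and selection on significance, and an estimation study that carries its estimate forward regardless of the p-value makes no such selection.

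**Conclusion.** This is a minor inconsistency of framing, and no change to the plan follows. The documents fit together as a randomised preliminary study whose estimate informs a confirmatory one. Twenty-five per arm is acceptable for that and exceeds the minimum that the SAP cites. No stated figure is wrong. The missing interval width is detail that the reported confidence interval will replace, and much of the protocol is written as though the trial has already been run. Aligning the wording, or reporting the difference with an interval, would restate the SAP's estimation purpose without altering the size, the data or any result.

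A sensible analyst would report the difference in the primary-outcome proportion with a 95% interval whatever the p-value, and would describe H.2.1 as preliminary. The expected half-width of about 16 to 25 points shows how preliminary.

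This rests on assumed uptake rates of 5% to 50%, a 95% interval and no missing primary outcomes. Statements about what the documents omit cover the visible text only. The conclusion would differ if either document claimed a power, a target difference or a confirmatory role for this trial; none does in that text.

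### No covariate is named for the uptake difference, although a pre-exposure score for self-efficacy, which the protocol links to uptake, is collected; a pre-specified adjusted estimate would be a cheap, modest improvement

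*SAP*

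**What the plan says.** The SAP's section on data analysis, design and power gives one primary quantity. It states that, at 25 per group, "we will have an adequate sample to estimate the difference in the proportion of participants who obtain GT between groups". It names no covariate, model, stratification factor or interval method. The size is not derived from a power or precision target: "the sample size calculation is based on practical considerations". The stated purpose is feasibility and effect sizes for a later confirmatory trial.

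The protocol's Detailed Description reports from the team's preliminary studies that "self-efficacy in making decisions about GCT and medical mistrust were associated with GCT uptake". The strength of that association is not given. The Secondary Outcome Measures table lists a Self-efficacy Scale ("The investigators tested self-efficacy in genetic counseling services"), scored in the hour before and the hour after exposure. The score appears only as a secondary outcome; nothing in the text reviewed uses its baseline value for the uptake comparison.

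**The concern.** The effect size is the main statistical product of this pilot. With 25 women per arm, the arms will often differ by chance on a score that predicts uptake. An unadjusted difference then carries part of that gap into the estimate handed to the confirmatory trial. The plan already collects a pre-exposure measure of a construct that it links to its primary outcome, so it could remove most of that component with one model term. Naming the covariate in advance would also prevent a later choice among several baseline measures.

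This is a different matter from adjusting each psychosocial scale for its own baseline value.

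**Working it through.** **Inputs from the documents.** 25 per arm, 50 in total (SAP and Detailed Description). A pre-exposure self-efficacy score (Secondary Outcome Measures). An association with uptake of unstated strength (Detailed Description).

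**Assumptions.** Overall uptake p of 20%, 30% or 50%. Odds ratio (OR) for uptake per SD of baseline score of 1.25, 1.5, 2 or 3, with OR 1 as the null case. None of these is in the documents.

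**1. The plan's own figure.** 2 x 25 = 50, and 25 exceeds the cited minimum of 12. No alpha, power, uptake rates or precision target is given, so 25 cannot be derived further. The precision it buys, unadjusted, is 1.96 x sqrt(2p(1-p)/25):
- p = 0.2: 1.96 x sqrt(0.0128) = 22.2 points
- p = 0.3: 1.96 x sqrt(0.0168) = 25.4 points
- p = 0.5: 1.96 x sqrt(0.0200) = 27.7 points

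**2. Chance imbalance.** The standardised difference in baseline means has SD sqrt(1/25 + 1/25) = sqrt(2/25) = 0.283, so its 95% range is ±1.96 x 0.283 = ±0.55 SD. The probability of an imbalance above 0.3 SD in either direction is 29%, and above 0.5 SD it is 8%.

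**3. Effect of an imbalance d on the unadjusted difference.** Take a logistic model with slope b = ln(OR) and intercept a set to give overall uptake p. With x standard normal, the shift is the mean over x of expit(a + b(x + d/2)) - expit(a + b(x - d/2)). R² is the share of the outcome variance explained by the score. The adjusted half-width is the unadjusted one times sqrt((1 - R²)(1 + 1/46)), where the last factor is the cost of estimating a slope.

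| p | OR | shift, d = 0.283 | shift, d = 0.5 | R² | half-width, unadjusted | half-width, adjusted |
|---|---|---|---|---|---|---|
| 20% | 1.25 | 1.0 | 1.8 | 0.008 | 22.2 | 22.3 |
| 20% | 1.5 | 1.8 | 3.2 | 0.026 | 22.2 | 22.1 |
| 20% | 2 | 2.9 | 5.2 | 0.071 | 22.2 | 21.6 |
| 20% | 3 | 4.2 | 7.4 | 0.156 | 22.2 | 20.6 |
| 30% | 1.25 | 1.3 | 2.3 | 0.010 | 25.4 | 25.5 |
| 30% | 1.5 | 2.3 | 4.1 | 0.033 | 25.4 | 25.3 |
| 30% | 2 | 3.8 | 6.6 | 0.087 | 25.4 | 24.5 |
| 30% | 3 | 5.3 | 9.4 | 0.181 | 25.4 | 23.2 |
| 50% | 1.25 | 1.6 | 2.8 | 0.012 | 27.7 | 27.8 |
| 50% | 1.5 | 2.8 | 4.9 | 0.038 | 27.7 | 27.5 |
| 50% | 2 | 4.4 | 7.8 | 0.098 | 27.7 | 26.6 |
| 50% | 3 | 6.2 | 11.0 | 0.198 | 27.7 | 25.1 |

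Shifts and half-widths are in percentage points.

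**4. Simulated estimators.** 40,000 trials of 25 per arm, 30% uptake, no effect, linear model with a common slope:

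| OR | SD unadjusted | SD adjusted | variance ratio |
|---|---|---|---|
| 1.25 | 0.1292 | 0.1299 | (0.1299/0.1292)² = 1.01 |
| 1.5 | 0.1292 | 0.1286 | 0.99 |
| 2 | 0.1296 | 0.1255 | 0.94 |
| 3 | 0.1300 | 0.1197 | 0.85 |

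The mean error of the unadjusted difference was 0.1 point or less. In trials with an imbalance near 0.5 SD, adjustment left an error under 1 point. Across the settings tried, the variance cut was about 5-8% at OR 2 and 8-17% at OR 3, and R² in the first table shows that the gain shrinks as uptake falls. At OR 1 to 1.25 the variance rose by up to about 2%.

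**5. Interval width.** 5,000 trials per setting, uptake 40% v 60%, HC3 standard errors both with and without the covariate. The mean half-width without the covariate is 27.7 points.

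| OR | adjusted half-width | adjusted interval narrower in |
|---|---|---|
| 1 | 28.3 | 13% of trials |
| 1.25 | 28.2 | 23% |
| 1.5 | 27.8 | 39% |
| 2 | 26.9 | 66% |
| 3 | 25.5 | 89% |

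A simple Wald interval averages 26.6 points, so part of any visible widening comes from HC3 itself. In a separate run of 6,000 trials per setting, coverage of the adjusted HC3 interval was 0.950 to 0.958.

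**The case against.** Four stronger readings are tempting, and the documents support none of them.

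- **That the plan chose a crude analysis.** The quoted sentence comes from a sample-size paragraph. The mention there of a test of proportions only supports the sample-size reasoning. A covariate-adjusted risk difference would also fit the words, and part of the SAP ahead of this section was not available for review. What can be said is that no adjustment is specified.
- **That imbalance biases the result.** Randomisation keeps the unadjusted difference unbiased, and its interval already allows for chance imbalance. The shifts above are conditional on the imbalance that happened to occur, and they are small against the interval.
- **That adjustment usually narrows the interval and costs nothing.** This holds only from about OR 2. With a weak or null predictor there is a small real loss.
- **That the scale is known to predict uptake.** The preliminary finding concerns decisions about counseling and testing, whereas the listed scale concerns counseling services. The instrument may differ.

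Two further objections stand in part. The protocol also names medical mistrust and anticipated negative emotions as correlates, so choosing self-efficacy involves judgement. It is, however, the correlate that most directly matches a listed pre-exposure scale. The control arm's pre-score also needs confirming: the arm table mentions pre and post assessments only under the video arm, while the Detailed Description refers to a baseline survey for participants generally.

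Finally, an unadjusted risk difference is a legitimate primary estimate for a 50-woman pilot. That is accepted, and it limits this point to a suggestion about efficiency and pre-specification.

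**Conclusion.** The point holds as a cheap improvement, not as the correction of an error. The gain depends wholly on an association whose strength the documents do not give. At OR 2, a variance ratio near 0.93 is like having 25/0.93 = 27 women per arm. At OR 3, a ratio near 0.85 is like 25/0.85 = 29. At OR 1.5 the gain is close to nil. At OR 1 to 1.25 the variance rises by up to about 2% and the HC3 half-width grows by about half a point (28.3 or 28.2 against 27.7).

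Apart from average precision, adjustment protects against an unlucky draw. With a 0.5 SD imbalance (8% of trials are at least this unbalanced), the unadjusted estimate at 30% uptake would be off by 2.3 to 9.4 points over OR 1.25 to 3, and adjustment removes nearly all of that.

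**What to change.** Add to the SAP a pre-specified risk difference by randomised arm, adjusted for the baseline self-efficacy score and reported beside the unadjusted difference. Either of two models would serve: a linear model for uptake with arm and score and HC3 standard errors, or a logistic model standardised to a risk difference. Fill a missing baseline score with the overall mean so that no woman is dropped. State which of the two estimates will feed the confirmatory trial's planning. If the sponsor prefers the unadjusted difference alone, one sentence saying so would close the gap.

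Before adopting the change, confirm that the pre-score is held for both arms and that the scale measures the construct found to be associated with uptake. Much of the protocol is in the past tense; if outcomes have already been seen, label the adjusted result post hoc.

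The cost is one or two SAP sentences and one model term, with no new data, plus the small loss of precision shown above if the score turns out to be a weak predictor.
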